7.4.1.4 Secondary Analysis of Primary Endpoint

The primary efficacy endpoint will also be analyzed using a Mixed Model Repeated Measure (MMRM). MMRM analysis will be conducted for change from baseline in the mean number of micturition episodes per 24 hours to post-baseline visits using the baseline the mean number of micturition episodes per 24 hours as a covariates, analysis visits and region as a fixed effect, subject as random effect and including interaction of [treatment group x visit] for FAS and PPS. For MMRM, Restricted Maximum Likelihood (REML) approach will be used, KENWARD-ROGER approximation will be used to estimate of degree of freedom of denominator, and ‘Unstructured’ will be assumed as structure of variance-covariance matrix. Though, when the calculation will not be converged, other covariance structures will be selected in the following order: ‘Unstructured Correlations’, ‘Heterogeneous Toeplitz’, ‘Heterogeneous First-Order Autoregressive’, ‘Toeplitz’, ‘First-Order Autoregressive’, ‘Compound Symmetry’, and ‘Variance Components’ instead. Within the framework of MMRM, point estimates and two-sided 95% CIs for the mean change from Baseline both within and between treatment groups (point estimate will be calculated as [Mirabegron + Tamsulosin] minus [PLACEBO + Tamsulosin]) will be calculated.

The SAS code used to implement MMRM will be similar to that shown below:

```
PROC MIXED method=REML;  
  CLASS treatment region visit usubjid;  
  MODEL chg = treatment region base visit treatment*visit / ddfm=KENWARDROGER;  
  REPEATED visit / type=UN subject=usubjid r;  
  LSMEANS treatment*visit / CL PDIFF=CONTROL("PLACEBO + Tamsulosin");  
RUN;
```

Here, variables in the MODEL statement are:

- chg: Change from baseline to End of Treatment in the mean number of micturitions per 24 hours
- treatment: Treatment group (PLACEBO + Tamsulosin/Mirabegron + Tamsulosin)
- region: Region (Japan/Korea)
- base: Baseline mean number of micturitions per 24 hours
- visit: Post-baseline visit (Week 4, Week 8, Week 12)
- usubjid: Subject Identifier

7.4.2 Analysis of Secondary Endpoints

The secondary endpoints are actual value and the change from Baseline to post-baseline and End of Treatment in:

- Mean number of micturations/24 hours (except for End of Treatment visit)
- Mean number of urgency episodes/24 hours
- Mean number of urgency incontinence episodes/24 hours
- Mean number of incontinence episodes/24 hours
- Mean number of nocturia episodes
- Mean volume voided per micturition
- Total OABSS score
- Subscale scores (daytime frequency, nighttime frequency, urgency and urgency incontinence) from OABSS score
- Total IPSS score
- Subscale scores (storage subscale, voiding subscale and quality of life item) and individual scores from IPSS score
- Symptom Bother and total Health-Related QoL scores, as assessed by the OAB-q questionnaire.

For the changes in mean number of incontinence and urge incontinence episodes, the analysis will be based on those subjects who have at least 1 incontinence episode at Baseline.

For the change in the mean number of nocturia episodes, the analysis will be based on those subjects who had at least 1 nocturia episode at Baseline.

Concerning actual value and the change from baseline to post-baseline of the secondary endpoints, descriptive statistics will be calculated by treatment group at each visit and at the End of Treatment for FAS and PPS.

Mean (+/- SD) plot for actual value and change from baseline to post-baseline will be presented by treatment group for FAS. In addition, for mean number of micturations/24 hours, this plot will be presented by subgroups defined in section 7.4.4 for FAS.

Radar charts of the mean of actual value for OABSS and IPSS will be made to present relationship between each question by treatment group for FAS.

For individual score from OABSS score and IPSS score, frequency tabulations of scores will be presented for each treatment group at each visit and at the End of Treatment for FAS and PPS.

Except for the changes in mean number of micturations, incontinence and urge incontinence episodes, change from Baseline to End of Treatment of these endpoints will be analyzed using an ANCOVA (refer to section 7.4.1.1 for detail) for FAS and PPS.

The changes from Baseline to End of Treatment in mean number of incontinence and urge incontinence episodes will be analyzed using a Stratified Rank Analysis of Covariance (RANCOVA), including the rank score for change from Baseline to End of Treatment stratified by region as the dependent variable, treatment group and region as fixed factors and the rank score for baseline stratified by region as a covariate for FAS

and PPS. The rank score is defined as fractional ranks by dividing each rank by the number of data + 1 and mid-ranks will be assigned for ties.

The SAS code used to implement RANCOVA will be similar to that shown below:

```
PROC RANK out=rank TIES = MEAN NPLUS1;
  BY region;
  VAR chg base;
  RANKS cr br;
RUN;
PROC GLM data=rank;
  CLASS region;
  BY region;
  MODEL cr = br / SS3;
  OUTPUT out = out residual = residual;
RUN;
PROC FREQ data = out;
  TABLE region*treatment*residual / CMH2;
RUN;
```

Here, variables in the MODEL statement are:

- chg: Change from baseline to End of Treatment in the mean number of micturitions per 24 hours
- base: Baseline mean number of micturitions per 24 hours stratified
- treatment: Treatment group (PLACEBO + Tamsulosin/Mirabegron + Tamsulosin)
- region: Region (Japan/Korea)
- cr: The rank of change from baseline to End of Treatment in the mean number of micturitions per 24 hours by region
- br: The rank score of baseline mean number of micturitions per 24 hours stratified by region

7.4.3 Analysis of Exploratory Endpoints

The exploratory endpoints include actual value and the change from Baseline to post-baseline and End of Treatment in:

- HUS
- First nighttime voided volume
- Subscale scores (coping, concern, sleep, social interaction) and individual scores from OAB-q

Concerning actual value and the change from baseline to post-baseline of these endpoints, descriptive statistics will be calculated by treatment group at each visit and at the End of Treatment for FAS.

Mean (+/- SD) plot for actual value and change from baseline to post-baseline will be presented for FAS.

For HUS, similar analysis will be done only for those subjects who have at least one micturition episode between sleep onset time and wake up time at baseline (e.x., IPSS Q7 > 0) or/and post-baseline. Descriptive statistics for HUS will be derived as the average of 2 consecutive nighttime diary. For example, if subject has only one night time episode in the 2 consecutive nighttime diary, average of HUS (time from sleep onset time to time of

first micturition episode) and HUS (time from sleep onset time to wake up time) will be calculated.

Kaplan-Meier curves will also be used to estimate the distribution of HUS for FAS. Median duration will be estimated using the corresponding 50th percentile of Kaplan-Meier estimates. A two-sided 95% confidence interval will be provided for this estimate. The 25th and 75th percentiles of Kaplan-Meier estimates, and the range of HUS (minimum, maximum) will be presented as well. The range will be determined including censored observations.

Conventions of censoring of HUS will be defined as; those subjects who have no micturition episode between sleep onset time and wake up time will be censored at wake up time. Also, similar analysis will be done treating them as subjects who have an event at the wake up time.

Radar charts of the mean of actual value for OAB-q will be made to present relationship between subscale scores by treatment group for FAS.

For individual score from OAB-q, frequency tabulations of scores will be presented for each treatment group at each visit and at the End of Treatment for FAS.

In addition, exploratory endpoints also include several normalization rates. The percentage of subjects normalized will be calculated excluding the subjects who were normalized at Baseline. The definition of normalization is as follows:

- OABSS: 1 point or less on Question 3, or a total score of ≤ 2 points
- Micturition episodes: mean number per 24 hours of < 8
- Urgency episodes: mean number per 24 hours of zero
- Urgency incontinence episodes: mean number per 24 hours of zero
- Incontinence episodes: mean number per 24 hours of zero
- Nocturia episodes: mean number per 24 hours of zero

The number and percentage of subjects who achieve normalization at the each visit and at the End of Treatment will be summarized along with 2 sided 95% CI (calculated by Clopper-Pearson method) for FAS.

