12.4 OABSS, OAB-q, IPSS and IPSS (QoL)

[figure not shown]
Overactive Bladder Symptom Score (OABSS):

Overactive Bladder Questionnaire (OAB-q):

International Prostate Symptom Score (IPSS):

In the past month:	Not at All	Less than 1 in 5 Times	Less than Half the Time	About Half the Time	More than Half the Time	Almost Always
1. Incomplete Emptying How often have you had the sensation of not emptying your bladder?	0	1	2	3	4	5
2. Frequency How often have you had to urinate less than every two hours?	0	1	2	3	4	5
3. Intermittency How often have you found you stopped and started again several times when you urinated?	0	1	2	3	4	5
4. Urgency How often have you found it difficult to postpone urination?	0	1	2	3	4	5
5. Weak Stream How often have you had a weak urinary stream?	0	1	2	3	4	5
6. Straining How often have you had to strain to start urination?	0	1	2	3	4	5
	None	1 Time	2 Times	3 Times	4 Times	≥5 Times
7. Nocturia How many times did you typically get up at night to urinate?	0	1	2	3	4	5

Quality of Life Due to Urinary Symptoms	Delighted	Pleased	Mostly satisfied	Mixed	Mostly dissatisfied	Unhappy	Terrible
If you were to spend the rest of your life with your urinary condition just the way it is now, how would you feel about that?	0	1	2	3	4	5	6

(GPF 4.1)

		Ver. 3.0	Ver. 4.0	Reason for amendment
1	SIGNATURES 1.SPONSOR'S SIGNATURE	ISN/Protocol 178-MA-3016, Version 3.0 Printed Name: [REDACTED]	ISN/Protocol 178-MA-3016, Version 4.0 Printed Name: [REDACTED]	Change of organization
2	CONTACT DETAILS OF KEY SPONSOR'S PERSONNEL	Corporate Name: Astellas Pharma Singapore Pte. Ltd. Location: [name] #22- 04 /05 [name] Phone No.: [REDACTED] Fax: [REDACTED] Sponsor's personnel: [REDACTED] Contact numbers during non-business hours and for emergency: Sponsor Personnel (Phone No) [REDACTED]	Corporate Name: Astellas Pharma Singapore Pte. Ltd. Location: [name] #22- 03 /05 [name] Phone No.: [REDACTED] Fax: [REDACTED] Sponsor's personnel: [REDACTED] Contact numbers during non-business hours and for emergency: Sponsor Personnel (Phone No); [REDACTED]	Change of organization

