Night time is the period between after sleep onset time and the wake-up time the following day (micturitions at the same time as the wake-up time will be excluded). The diary must be completed for at least 2 consecutive days to allow assessment of night time frequency for at least 1 night. Any data collected before the wake-up time on the first day of diary completion and after the sleep onset time on the third day cannot be included in the assessment of night time frequency. Only those subjects whose symptoms were confirmed at baseline (Visit 2) will be analyzed.
If there is no nocturia episode on all evaluable night time in each visit, then the mean number of nocturia episodes/24 hours is equal to zero. Therefore if the mean number of nocturia episodes per 24 hours is “0” at baseline, this subject is excluded from the analysis.

- Mean volume voided per micturition
Calculation is similar to ‘micturition’, but sum urinary volumes where the volume voided is > 0 and where ‘Urinary incontinence’ is not indicated, rather than count the episodes. The denominator will be the number of micturitions where the volume voided is > 0 and where ‘urinary incontinence’ is not indicated. Only those subjects whose symptoms were confirmed at baseline (Visit 2) will be analysed.

- Total OABSS score
For each patient, OABSS total score will be the sum total of the score of each item (Questions 1-4).
- Subscale scores (daytime frequency, nighttime frequency, urgency and urgency incontinence) from OABSS score
For each patient, OABSS subscale scores will be the score of each item (Questions 1-4).
- Total IPSS score
For each patient, total IPSS score will be the sum total of the score of each item (Questions 1-7).
- Subscale scores (storage subscale, voiding subscale-1, voiding subscale-2 and quality of life item) and individual scores from IPSS score
For each patient, IPSS subscale scores will be calculated by following each formula. Storage subscale is derived as sum of scores for questions 2, 4, and 7. Voiding subscale-1 is derived as sum of scores for questions 3, 5, and 6. Voiding subscale-2 is derived as sum of voiding subscale-1 and the score for question 1.
For each patient, Individual scores and IPSS QoL score will be the score of each item (Questions 1-7 and quality of life item).

- Symptom Bother and Total Health-Related Quality of Life scores (Total HRQL scores), as assessed by OAB-q

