6.1.3 Exploratory Efficacy Endpoints

The exploratory endpoints will include the change from Baseline to post baseline and End of Treatment in:

- Hours of undisturbed sleep (HUS)

For each patient, hours of undisturbed sleep (HUS) will be calculated by visit and night. Only those subjects whose symptoms were confirmed at baseline (Visit 2) will be analyzed, therefore if IPSS Q7 score is “0” at baseline, this subject is excluded from the analysis.

HUS is calculated as time from sleep onset time to time of first micturition episode (the variable ‘Urinary incontinence’ or ‘Urgency’ is NOT indicated and after the time of sleep onset time) only if the diary completed for 3 consecutive days is available. On the other hand, for those subjects who have no micturition episode between after sleep onset time and wake up time, HUS is calculated as time from sleep onset time to wake up time.

If the interval between sleep onset time and wake up time is more than 24 hours, HUS will be calculated as follows:

HUS is calculated as time from sleep onset time to time of first micturition episode (the variable ‘Urinary incontinence’ or ‘Urgency’ is NOT indicated and after the time of sleep onset time) only if the diary completed for 3 consecutive days is available and the time of first micturition episode is before AM.5:59 of the next day of sleep onset. On the other hand, for those subjects who have no micturition episode between after sleep onset time and AM.5:59 of the next day, HUS is null.

- First nighttime voided volume

For each patient, urinary volume at the first nighttime (between after the time of sleep onset and wake up time + 30 minutes) will be calculated. Only those subjects whose symptoms were confirmed at baseline (Visit 2) will be analysed.

If the interval between sleep onset time and wake up time is more than 24 hours, first nighttime voided volume will be calculated as follows:

For each patient, urinary volume at the first nighttime (after the time of sleep onset and before AM.5:59 of the next day) will be calculated. On the other hand, for those subjects who have no micturition episode between after sleep onset time and AM.5:59 of the next day, urinary volume at the first nighttime is null. Only those subjects whose symptoms were confirmed at baseline (Visit 2) will be analysed.

- Subscale scores (coping, concern, sleep and social interaction) and individual scores from OAB-q scores

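### The additional analysis of hours of undisturbed sleep (HUS) picks its subset partly by night voiding after treatment, through an unresolved 'or/and'; the subset should be fixed by baseline data alone

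*SAP*

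**What the plan says.** SAP 7.4.3 plans descriptive statistics and mean plots of HUS for the FAS. It then adds that "similar analysis will be done only for those subjects who have at least one micturition episode between sleep onset time and wake up time", and completes the condition with "at baseline (e.x., IPSS Q7 > 0) or/and post-baseline". It does not say whether *or* or *and* is meant, which post-baseline visit counts, or whether the IPSS item is the criterion or only an example. It continues: "Kaplan-Meier curves will also be used to estimate the distribution of HUS for FAS". Men without a night void are censored at wake-up there, and a repeat counts wake-up as the event. No between-arm test of HUS is specified.

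SAP 6.1.3, which defines the endpoint, has a baseline condition only: "Only those subjects whose symptoms were confirmed at baseline (Visit 2) will be analyzed, therefore if IPSS Q7 score is" zero at baseline, the man is left out. For a man with no night void, "HUS is calculated as time from sleep onset time to wake up time", so a man whose nocturia resolves has a defined and long HUS.

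The neighbouring nocturia endpoint in SAP 6.1.2 confirms baseline symptoms by diary: "Therefore if the mean number of nocturia episodes per 24 hours is" zero at baseline, the man is excluded. IPSS question 7 (Protocol 12.4) asks "How many times did you typically get up at night to urinate", with the past month as its recall period.

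**The concern.** Randomisation balances the arms on what is known before treatment. A subset chosen partly by a post-treatment event loses that protection, most directly when the event is the one the endpoint measures. If mirabegron abolishes night voiding in some men, a rule requiring a later night void drops more men from the mirabegron arm, and drops those with the longest HUS. The difference that remains describes men in whom the drug worked less well.

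The ambiguity matters in its own right. Protocol 7.4.3 leaves the detail of the exploratory analyses to the SAP. As written, whoever programs the table must choose between populations that can give different answers. Because no post-baseline visit is named, membership could also change from visit to visit.

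**Working it through.** **Plan's own figure.** The documents give no HUS effect, SD or power. Their only design figure is for the primary endpoint: difference 0.7, SD 2.4, two-sided 5%, 90% power. It reproduces: 2 × (1.960 + 1.282)² × 2.4² / 0.7² ≈ 247.1, rounded up to 248 per arm. It has no bearing on HUS.

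**Step 1: who is in the subset.**

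| Night void at baseline | Night void after treatment | *or* | *and* | Baseline only |
|---|---|---|---|---|
| yes | yes | in | in | in |
| yes | no (resolved) | in | **out** | in |
| no | yes (new) | **in** | out | out |
| no | no | out | out | out |

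Under *and*, men with a baseline void are divided by their outcome. Under *or*, men without a baseline void are divided by theirs. Only the last column is settled before treatment. Selecting on post-baseline voiding alone would also drop resolved men, but that reading ignores the words about baseline.

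**Step 2: possible size, on assumed values.** Time to first void on a given night is exponential, with mean 3.0 h at baseline and 3.3 h on placebo after baseline, and varies between men. Sleep lasts about 7.5 h, and two nights are averaged. The mirabegron-to-placebo ratio of mean time to first void is set at 1.25, 1.5 or 2.0. None of these values comes from the documents. Between-arm difference in HUS change, simulated:

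| Ratio | Baseline only | *or* | *and* | Attenuation under *and* |
|---|---|---|---|---|
| 1.25 | 0.44 h | 0.44 h | 0.39 h | 1 − 0.39/0.44 = 11% |
| 1.5 | 0.81 h | 0.81 h | 0.70 h | 1 − 0.70/0.81 = 14% |
| 2.0 | 1.40 h | 1.40 h | 1.18 h | 1 − 1.18/1.40 = 16% |

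The *and* rule keeps 96.0% of placebo men against 94.3%, 92.3% and 87.7% of mirabegron men. With no drug effect (ratio 1.0), every rule gives a difference of zero. In this model 98.2% of men void at night at baseline, so it says little about the *or* rule in a population where many do not.

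**Step 3: a deliberate extreme.** Suppose 10% of placebo and 20% of mirabegron men resolve, each gaining 4 h, and all others gain 0.5 h in both arms.

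- Resolved men kept: (0.20 × 4 + 0.80 × 0.5) − (0.10 × 4 + 0.90 × 0.5) = 1.20 − 0.85 = 0.35 h.
- Resolved men removed: 0.5 − 0.5 = 0 h.

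The loss is total only because resolution was made the whole benefit.

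**Step 4: the baseline filter.** SAP Table 1, footnote d, places randomisation after all other Visit 2 procedures, and Protocol 5.1.5 has the first tablet taken the day after dispensing. IPSS question 7 at Visit 2 therefore cannot reflect treatment. It can disagree with the diary. A man scoring above zero with no diary void already has full-sleep HUS and little room to improve, and a man scoring zero with diary voids is dropped.

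**Step 5: which void counts.** In 6.1.3 the HUS event is the first void with neither urgency nor incontinence marked. The selection in 7.4.3, and the nocturia count in 6.1.2, take any void. A man whose night voids are all marked urgent passes the selection but has no qualifying HUS event.

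**The case against.** The natural sense of the phrase is an inclusive *or*: a void at baseline, afterwards, or both. On that reading resolved men stay, and the illustration matches baseline-only selection to two decimals. Moreover, if 6.1.3 governs and the IPSS item is itself the baseline criterion, men scoring zero are already out, and *or* adds nobody. This stands as a limit on the likely harm. It does not settle the text, which supports *and* equally well on its face, nor does it make a post-baseline condition useful.

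A reader might infer that the plan hides an effect on sleep. The documents do not support that. The FAS summaries of HUS set no post-baseline condition, the Kaplan-Meier analyses keep men without a night void, and the nocturia normalisation rate in 7.4.3 counts resolution directly. A reader might also infer that the IPSS filter removes responders. It cannot, because it is applied before treatment.

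It can also be said that preferring the diary to the IPSS item is partly taste. Two diary nights are noisy, and selecting on the diary that supplies baseline HUS invites regression to the mean. That is fair. Such regression would be expected in both arms alike, and the choice of instrument matters less than using one criterion throughout.

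**Conclusion.** The concern holds for the additional HUS analysis in SAP 7.4.3. Its population is ambiguous, and every reading that uses the post-baseline condition selects on the outcome. Under *and*, attenuation is about 11% to 16% on the assumed values and greater if most of the benefit is resolution. Under *or*, none appears on those values, although entry still depends on outcome for men without a baseline void. These sizes are illustrations and not estimates for this trial.

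The consequence is limited to one descriptive, exploratory analysis. The primary endpoint, the secondary endpoints and the other HUS outputs are untouched.

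The mismatch between the IPSS item and the diary is a separate, minor matter of definition. It leaves the randomised comparison unbiased, but the HUS and nocturia endpoints describe somewhat different men. It is also unclear whether the FAS summary of HUS in 7.4.3 is meant to be unselected, since 6.1.3 restricts the endpoint.

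**What to change.** - In SAP 7.4.3, delete the post-baseline condition so that membership is fixed by Visit 2 data and is the same at every visit.
- State one baseline criterion and use it in both 6.1.3 and 7.4.3. At least one night void in the Visit 2 diary would be in line with the nocturia endpoint; an IPSS question 7 version can be kept as a sensitivity analysis.
- Reconcile the two sections by making the FAS summary of HUS the unselected version and the baseline-nocturia subset the restricted one. The exclusion should then move out of the endpoint definition in 6.1.3 and into the description of the subset.
- Make the qualifying night void match the HUS event, so that voids marked with urgency or incontinence are treated alike in both.

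The cost is a few lines of SAP text and one population flag, settled before unblinding. No new data are needed and no sample size changes.
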